## Tool Revision History

Version Number: 1.2

Version Date: 03 May 2022

Summary of Revisions Made: Made reliance IRB pre-screen revisions (see 4.3, 13.1, and 13.2)

Version Number: 1.3

Version Date: 09 May 2022

Summary of Revisions Made: Made minor revisions to wording of inclusion criteria and recruitment procedures. Also fixed grammatical and spelling errors

Version Number: 1.4

Version Date: 07 Jul 2022

Summary of Revisions Made: Minor revisions to treatment details (see 5.1) and methods for assessing adverse events related to suicide assessments (see 7.1)

Version Number: 1.5

Version Date: 31 Aug 2022

Summary of Revisions Made: Removal of some self-report instruments (see 6.2) that will be given to patients. Description of instruments (see 6.3) has been updated accordingly.

Version Number: 1.6

Version Date: 11 Jan 2023

Summary of Revisions Made: Updated adverse event reporting procedures (see 7.3) to include reporting to TMS device manufacturer. Changed age range in inclusion criteria (see 4.1) and added pre-consent screening instrument (see 4.3)

Version Number: 1.7

Version Date: 23 Mar 2023

Summary of Revisions Made: Made various updates to timing and inclusion of certain study evaluations to better capture patient symptom change (see 6.2). Changed definition of immediate follow up throughout entire protocol (changed from 3-5 days to up to 5 days). Made consistent/clarified instruments that assess suicidality (see 7.1). Updated age in study synopsis to be consistent with inclusion/exclusion criteria

Version Number: 1.8

Version Date: 19 Apr 2023

Summary of Revisions Made: Updated schedule of screening visit to all participant's to be on a sufficient medication or medication dose as required by inclusion criteria 4 and 5 (see 6.1, 6.2). Participant reimbursement method is further specified (see 3).

## STUDY SYNOPSIS

Title	A Pilot Study of iTBS in Bipolar I Depression
Source of Funding	Baszucki Brain Research Fund
Study Population	Participants aged 18+ years old with a diagnosis of bipolar I disorder, current episode depressed
Study Design	A multisite, open label pilot study to investigate the efficacy and safety of a novel accelerated intermittent theta-burst stimulation (iTBS) protocol while assessing for changes in neuroimaging biomarkers associated with treatment response
Primary Objectives	To examine the use of accelerated iTBS to treat symptoms of treatment resistant depression in bipolar I disorder and assess changes in neuroimaging biomarkers that may predict treatment response.
Number of Sites	2
Total number of Participants	10 (5 at each site)
Study Duration	1 year

## ABSTRACT

Intermittent theta-burst stimulation (iTBS) is a patterned form of repetitive transcranial magnetic stimulation (rTMS), an effective, neuromodulatory treatment for refractory depression. Accelerated rTMS paradigms have become of increasing clinical interest to address the potential limiting factors of dose response variability and the burden that standard rTMS treatment poses due to the requirement of weeks of treatment at great financial expense. Even with reduced treatment time in iTBS compared with standard rTMS, there remains a barrier in requiring weeks or months of daily treatment sessions for desired response. A recent study carried out by members of our collaborative study team assessed the safety, tolerability and efficacy of an accelerated iTBS protocol and found a 90% antidepressant response in individuals with treatment resistant depression (TRD), in only 5 days (Cole et al., 2020, 2022) This proposed pilot study intends to use this novel accelerated iTBS approach for TRD in bipolar disorder, while assessing changes in neuroimaging biomarkers that are associated with treatment response. It will provide feasibility data to lead to development of a larger, multisite, adequately powered study of this treatment approach and factors associated with treatment response through collaborations within nodes of the National Network of Depression Centers (NNDC), a consortium of academic centers of excellence providing care for participants with mood disorders.

## 1. STUDY OBJECTIVES

### 1.1 Primary Objective

To examine the use of accelerated iTBS to treat symptoms of treatment resistant depression in bipolar I disorder and assess changes in neuroimaging biomarkers that may predict treatment response:

Primary Outcome Measure: Change in Montgomery-Asberg Depression Rating Scale (MADRS) score.

Secondary Outcome Measure: Changes in MRI derived functional connectivity of the subcallosal cingulate to the DLPFC and within the default mode network.

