### **Neuroimaging Biomarkers:**

We will perform structural and resting state functional connectivity MRI with a 3T system prior to active study phase and immediately after active study phase (up to 5 days following final iTBS stimulation). The MRI scans will require about 1 hour in the MRI scanner. During the scan, participants will lie on the table in the magnet while the images are acquired. Instructions may be given through an auditory system. Subjects will wear earplugs and may be fitted for a bite bar to help them to keep their head still during the scans; for studies that enroll older adults, a bite bar will not be used so as to accommodate participants with dentures. These procedures have been used previously in younger and older adults alike, and do not cause undue distress in subjects.

At Baseline and 1 week, our MRI scans will include:

- Anatomical (T1) - 5min
- Resting state fMRI - 24 min
- Resting state ASL - 7 min

-Diffusion-weighted imaging (DWI) - DWI acquisition will take approximately 4 min along 90 non-collinear directions with a b-value=2400s/mm^2.

TOTAL scan time: ~40min

Biomarker measures: We will use a canonical hemodynamic response function (HRF) convolved event-related model with temporal and dispersion derivatives to model the blood oxygen level dependent (BOLD) in the context of a generalized linear model. Separate regressors (convolved with the HRF) will be created for stimulus events in each paradigm. Temporal and dispersion derivatives will be treated as regressors of no interest. A region of interest (ROI) analysis will be performed using our established methods, to identify BOLD-dependent signal change in the dorsolateral prefrontal cortex, subgenual cingulate, and default mode network nodes (right, left). Beta values for each ROI will be extracted for each subject for regression analyses.

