## 9.4 Data Analyses

The primary outcome measures will be analyzed using generalized linear mixed models to test if there are significant changes in scores over follow-up. Based on previous work, we will use a compound symmetry or autoregressive covariance structure (based on distribution of residuals) and robust estimation of coefficients to handle violations of model assumptions. Random effects will be included to account for repeated measures on the same participants, and fixed effects of time will be evaluated controlling for fixed effects of age, sex and number of days to reach treatment remission. All post hoc pairwise comparisons will be Bonferroni corrected. Exploratory endpoints related to biometrics will be analyzed in similar fashion.

For assessment of the secondary outcome measures of change in functional connectivity, we will employ a resting-state seed-based functional connectivity approach to assess connectivity between the subcallosal cingulate connectivity to the DLPFC and within the default mode network. For each participant, the correlation coefficients between average blood oxygen level-dependent (BOLD) time series of the seed-region and the BOLD time series of each grey matter voxel within the DLPFC or default mode network will be calculated. The correlation coefficient will be converted to normally distributed z scores by the application of Fisher's r to z transformation. The resulting connectivity maps will be analyzed with repeated measures ANOVA to compare pre-iTBS vs post-iTBS connectivity measures as a within-subject variable, and sex and site as a between-subject covariate.

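### No specified analysis relates imaging to MADRS outcome, and the regression step in 5.1 rests on an event-related model that the listed resting-state scans cannot support

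*Combined protocol and SAP*

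**What the plan says.** **Aim.** The synopsis and section 1.1 include in the primary objective the intention to "assess changes in neuroimaging biomarkers that may predict treatment response". The abstract describes the pilot as "assessing changes in neuroimaging biomarkers that are associated with treatment response". Section 1.1 then names the imaging measure as a secondary outcome: "Changes in MRI derived functional connectivity of the subcallosal cingulate to the DLPFC and within the default mode network".

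**Analysis in 9.4.** Connectivity is computed from a resting-state seed, Fisher-z transformed, and put into a repeated measures ANOVA "to compare pre-iTBS vs post-iTBS connectivity measures as a within-subject variable, and sex and site as a between-subject covariate". The mixed model for MADRS and YMRS has time, age, sex and days to remission.

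**Analysis in 5.1, Neuroimaging Biomarkers.** This paragraph describes an event-related haemodynamic model: "Separate regressors (convolved with the HRF) will be created for stimulus events in each paradigm". It ends: "Beta values for each ROI will be extracted for each subject for regression analyses". The scan list in the same section has an anatomical T1, "Resting state fMRI - 24 min", a resting-state ASL run and diffusion imaging.

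**Timing.** The schedule in 6.1 has MRI at baseline and at the immediate follow-up only. Section 9.3.2 defines the secondary outcomes as change from baseline to 1 month.

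**The concern.** A test of mean change in connectivity shows whether the group shifted. It does not show whether participants with a particular baseline value, or a particular shift, did better on MADRS. The aim in the synopsis, abstract and 1.1 is about that second question, and no model in the plan addresses it.

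The 5.1 regression step might have been meant to do so. However, it names no outcome or covariates, and it takes its input from a model that needs stimulus onsets, which resting-state runs do not have.

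Two things are at stake. Followed literally, the plan leaves the response-related part of the aim unanswered. If the analyst improvises instead, the choice of region, summary, outcome and time point would be made after the data are seen, in 10 participants, with obvious room for selective reporting.

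**Working it through.** The plan states no figure on this point to reproduce. The sample size of 10 rests on feasibility (9.1), and no alpha or power is given. The check is mainly a reading of the text, with arithmetic for scale.

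**1. Is there any term linking imaging to outcome?**

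| Analysis | Outcome | Terms | Link to MADRS |
|---|---|---|---|
| 9.4 connectivity ANOVA | connectivity | pre/post, sex, site | none |
| 9.4 mixed model | MADRS, YMRS | time, age, sex, days to remission | no imaging term |
| 5.1 regressions | not named | ROI betas | not stated |

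The response definition (a fall of at least 50% in MADRS) is used in 6.2 and section 8 for referral, and in no analysis.

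**2. Can the 5.1 betas be computed?** The listed scan times are 5 + 24 + 7 + 4 = 40 minutes, equal to the stated total of about 40. No time is left for a task run. The CANTAB tests are done on a tablet (6.2). Exclusion criterion 9 mentions a neutral memory task, but none appears in the scan list or the schedule. The only BOLD run is resting state, so there are no events to convolve.

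**3. Does the pre/post test carry information on association?** Simulation: n = 10, 40,000 runs, a two-sided 5% t test on the connectivity change (sex and site omitted). The change is m + rho·d + sqrt(1 - rho²)·e, where d is the standardised MADRS change and e is independent noise.
- m = 0.5 SD, rho = 0: rejects in 29.7% of runs.
- m = 0.5 SD, rho = 0.7: rejects in 29.4%.
- m = 0, rho = 0.7: rejects in 4.8%, about the nominal rate.

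The test responds to the mean shift and is blind to the association.

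**4. What could 10 participants show?** The 95% interval is tanh(atanh(r) ± 1.96/sqrt(n - 3 - k)), with k covariates. The r values are illustrative.
- r = 0.6, k = 0: 0.693 ± 0.741, giving -0.05 to 0.89.
- r = 0.6, k = 1: 0.693 ± 0.800, giving -0.11 to 0.90.
- r = 0.8, k = 0: 1.099 ± 0.741, giving 0.34 to 0.95.

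At an assumed two-sided alpha of 0.05, 80% power needs a true r of tanh((1.96 + 0.84)/sqrt(7)) = 0.79.

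**5. Responder status or continuous MADRS?** At the 90% response rate cited in the abstract, 10 × 0.1 = 1 non-responder is expected. The chance of at most one is 0.9^10 + 10 × 0.1 × 0.9^9 = 0.349 + 0.387 = 0.74. A responder comparison could well rest on one person, so continuous MADRS is the usable outcome.

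**6. Why adjust for baseline MADRS?** Treatment stops at MADRS of 10 or less (6.2) and entry requires at least 20 (4.1). Two participants who start at 20 and 34 and both end at 10 change by 10 and 24 points. That difference is entirely baseline severity. An unadjusted association between baseline connectivity and MADRS change could therefore be a severity artefact.

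**The case against.** The best defence is that the objective is hedged. Its verb is to assess changes, the predictive clause only describes candidate markers, and 1.1 makes the measure a secondary outcome that 9.4 does test. This stands in part. A reader might infer that half of the primary objective fails, but the documents do not support that, because the change component has a coherent analysis. The component on prediction or association with response still has none.

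A reader might also infer that the larger trial depends on a biomarker-response estimate from this pilot. The abstract promises feasibility data, and 9.1 adds preliminary data to motivate further study. Neither makes such an estimate a required input.

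A third tempting reading is that connectivity change cannot predict any response, because the second scan falls at the immediate follow-up, where the primary MADRS endpoint is also taken. That holds for the immediate endpoint only. MADRS is collected again at 1 month, after the second scan, so connectivity change could precede later outcome.

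The mention of regression in 5.1 does suggest that an association analysis was intended, and 9.4 gives an analyst a workable resting-state method, which limits the harm from the 5.1 text. Intent without a named outcome, and with inputs that cannot be obtained, is still not a specification.

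Finally, 10 participants are too few for a formal prediction test. That is correct, and it argues for estimates with intervals. It does not argue for leaving the analysis undefined.

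**Conclusion.** The point holds in this form: the plan states an aim about imaging and treatment response, specifies no analysis relating the two, and includes in 5.1 an event-related method that does not fit its own scan list or the seed-based method in 9.4. A related inconsistency is the 1-month secondary window in 9.3.2, for which no MRI is scheduled.

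The consequence is limited. The primary MADRS analysis and the pre/post connectivity test are unaffected. What is missing is a pre-specified description of association, which at n = 10 would be imprecise (step 4 above). The change should be made, but the trial's main result does not depend on it.

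The conclusion rests on the scan list being complete, which its matching time total supports. The power figure assumes a two-sided alpha of 0.05, and the correlations are illustrative.

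**What to change.** - **5.1:** replace the event-related and beta text with the seed-based resting-state measure of 9.4. For the association analysis, extract one mean Fisher-z value per participant and scan for subcallosal cingulate to DLPFC, and one for within the default mode network. Keep the pre/post map analysis.
- **9.4:** add exploratory estimates for each measure, with 95% intervals and no significance claim:
  - (a) baseline connectivity against MADRS at the immediate visit, adjusted for baseline MADRS (prediction);
  - (b) connectivity change against MADRS change to the immediate visit, adjusted for baseline MADRS (a concurrent correlate, not a predictor);
  - (c) optionally, connectivity change against 1-month MADRS.
- **9.3.2:** set the imaging window to baseline to the immediate follow-up scan.
- **1.1 and synopsis:** word the aim to match these analyses.

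The cost is wording in four places and a small amount of analysis. No scans, visits or participants are added. The drawback is that the intervals will be wide, slightly wider still with adjustment, and the report must say that the results are descriptive only.

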## 2. BACKGROUND AND RATIONALE

### 2.1 Background on Condition, Disease, or Other Primary Study Focus

Bipolar disorder is a chronic and burdensome illness that affects up to 5% of adults (Merikangas et al., 2011) and is associated with direct and indirect costs of care exceeding \$200 billion annually in the US (Cloutier et al., 2018). Individuals with bipolar disorder spend considerably more time ill with depression than with mania or hypomania symptoms (Miller et al., 2014), such that depression accounts for the majority of the time spent unwell. Bipolar disorder is associated with high rates of morbidity and mortality and is an important contributor to long-term dysfunction due to psychosocial impairment, loss of work productivity and high rates of substance abuse (McIntyre & Calabrese, 2019). Compared to the general population, individuals with bipolar disorder are at greater risk to attempt and complete suicide, especially among individuals experiencing longer periods of depression than mania (Baldessarini et al., 2006). First line treatments for depression are limited in bipolar disorder, and treatment resistance can be up to two times higher when compared to unipolar depression (Tondo et al., 2014).

### 2.2 Study Rationale

Repetitive transcranial magnetic stimulation (rTMS) is a safe, neuromodulatory clinical intervention used to treat depression. When stimuli are applied to the left dorsolateral prefrontal cortex (LDLPC), rTMS has been shown to be safe and effective in treating individuals with both unipolar and bipolar depression (Kazemi et al., 2018; Rachid et al., 2017). Accelerated rTMS paradigms have recently been explored to determine the safety, tolerability, and efficacy of delivering multiple sessions over fewer days, to achieve similar outcomes compared with a standard series of rTMS (Sonmez et al., 2019). Reducing treatment time is important not only to reduce individuals' suffering and resource strain, but also to address accelerating antidepressant response in more severely depressed individuals who are at greater risk for suicide. Intermittent theta burst stimulation (iTBS) is a form of patterned rTMS, recently deemed "non-inferior" to standard rTMS in the treatment of unipolar major depressive disorder (Blumberger et al., 2018; Chung et al., 2015). Even with a significant benefit in reduced treatment time in iTBS compared with the standard rTMS treatment time of 4-6 weeks, time constraints, transportation, and the financial resources to attend daily sessions over weeks of time remain cumbersome limitations (Bakker et al., 2015). Moreover, as individuals with bipolar disorder tend to have more treatment resistance and spend more time in a depressed state with higher risk for suicide the value of non-invasive treatment options is emphasized.

A recent study carried out by members of our collaborative study team developed an accelerated iTBS treatment paradigm called Stanford Accelerated Intelligent Neuromodulation Therapy (SAINT). SAINT utilized prior evidence to further enhance the

propensity of antidepressant response to iTBS by modifying parameters in pulse spacing, dosage and treatment target location (Cazzoli et al., 2009, 2012; Fox et al., 2012; Gamboa et al., 2010; Noh et al., 2012). Applied in a sample of individuals with unipolar (n=20) and bipolar (n=5) treatment resistant depression (TRD), the use of an accelerated iTBS paradigm yielded approximately 90% response and remission rates in depressive symptoms, in both unipolar and bipolar TRD participants (Cole et al., 2020). Of the 5 bipolar TRD participants, all met depression remission criteria within 5 days of treatment, with no hypomania/mania conversion observed during treatment or at follow-up. More recently, SAINT demonstrated evidence of efficacy over sham stimulation in RCT for treatment-resistance depression (Cole et al., 2022). The current study aims to further evaluate the use of an adapted accelerated iTBS protocol for bipolar TRD and neuroimaging biomarkers of treatment response. It will leverage the resources of the National Network of Depression Centers (NNDC), a consortium of academic centers of excellence caring for participants with depression and bipolar disorder, to conduct the pilot study.

### **3. STUDY DESIGN**

In order to establish feasibility of study design and approach, we will conduct an open label pilot trial of treatment using accelerated iTBS over the left dorsolateral prefrontal cortex (LDLPC) (up to five days, up to 10x/day) using the MagVenture MagPro X100 rTMS System. Participants will have individualized treatment targets that will be produced from structural and functional MRI scans using the software services of Magnus Medical. We will enroll a total of 10 outpatient participants at two participating NNDC centers, the Johns Hopkins University and University of Texas at Austin. The participants will be diagnosed with bipolar I disorder, currently depressed, as determined by a SCID-5 assessment at screening [Day -5/-14]. Participants will be asked to remain on their psychotropic medications for stabilization throughout the screening, baseline, active study and follow-up phases of the study. During active study, changes in medication dosages may be made based on clinical judgment as outlined below. Participants will be required to have an established psychiatrist in order to facilitate ongoing care after the trial.

The expected overall study duration is one year. Each patient will have up to 9 total visits over the course of one month. One visit for consent and screening. One visit for baseline clinical and self-report assessments, MRI scan, and neurocognitive tests. Five consecutive day visits (or less per symptom remission as outlined above via MADRS </=10) of 10 hours each for treatment. Two visits for follow-up. One immediately (up to 5 days) after last day of treatment for clinical and self-report assessments, MRI scan, and neurocognitive tests. And another visit 1-month post-treatment visit for clinical and self-report assessments. All costs for the clinical assessments, MRI scans and TMS treatment related to the conduct of the study will be covered by the study at no expense to the patient. Participants will receive \$500 compensation upon completion of last follow up appointment. This study will offer participants a choice to receive payment/reimbursement through the JHU Greenphire ClinCard Program. The standard Greenphire information sheet will be used to explain the use of Greenphire to participants.

## 4. SELECTION AND ENROLLMENT OF PARTICIPANTS

### 4.1 Inclusion Criteria

1. 18+ years of age
2. Bipolar I disorder diagnosis as defined by The Diagnostic and Statistical Manual of Mental Disorders, Fifth Edition (DSM-5)
3. Currently experiencing a Major Depressive Episode with Montgomery-Asberg Depression Rating Scale (MADRS)  $\geq 20$  at screening [Day -5/-14] and baseline [Day 0]
4. On a stable and adequate dose of an anti-manic agent (Lithium with a level of at least 0.6, Depakote with a level of at least 50, or a therapeutic dose of carbamazepine, oxcarbazepine, or a neuroleptic for treatment of mania per clinician judgment) without dose changes for at least 6 weeks prior to the active study time period. Final assessment of appropriateness of participant's pharmacologic regimen is subject to study team clinician judgment.
5. Having failed a therapeutic trial of a first line bipolar depression antidepressant (as specified by the Antidepressant Treatment History Form and updated with new medications approved by the FDA for treatment of bipolar depression) in this current episode. This includes a minimum 4 week trial of one of the following medications (minimum dosage): lithium 900mg daily (or blood level  $\geq 0.6$  mEq/L), carbamazepine 400mg daily (or blood level  $\geq 0.8$  mEq/L), lamotrigine 200mg daily, asenapine 20mg daily, lurasidone 20mg daily, olanzapine 10mg daily, quetiapine 300mg daily, or lumateperone 42mg daily. Final determination of a failed adequate therapeutic trial is subject to study team clinician judgement.
6. Established outpatient psychiatrist

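### Inclusion criterion 5 states the carbamazepine adequacy level in mEq/L, a unit that does not apply to an uncharged drug, so the level cannot be applied as written (minor, narrow effect)

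*Combined protocol and SAP*

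**What the plan says.** Section 4.1, item 5 requires that a first-line treatment for bipolar depression has failed in the current episode. The rule is "This includes a minimum 4 week trial of one of the following medications (minimum dosage", followed by eight drugs. Most carry a dose only. Two carry a dose or a blood level:

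- Lithium: "lithium 900mg daily (or blood level $\geq 0.6$ mEq/L".
- Carbamazepine: "carbamazepine 400mg daily (or blood level $\geq 0.8$ mEq/L".

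The item takes its adequacy standard from a named instrument: "as specified by the Antidepressant Treatment History Form and updated with new medications approved by the FDA for treatment of bipolar depression". It closes with an override: "Final determination of a failed adequate therapeutic trial is subject to study team clinician judgement".

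Carbamazepine also appears in item 4, as an anti-manic agent, but without any level: "a therapeutic dose of carbamazepine, oxcarbazepine, or a neuroleptic for treatment of mania per clinician judgment".

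**The concern.** Item 5 is the only entry criterion in Sections 4.1 and 4.2 that puts treatment resistance into practice, and treatment-resistant bipolar I depression is the population in the stated objective (Section 1.1). A threshold in that criterion should be one that a rater can check against a laboratory report.

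The carbamazepine level is not. It carries the unit of the lithium entry beside it, and that unit does not fit the drug. Because the level is joined to the dose by an *or*, it is a separate route to adequacy for someone who took less than 400 mg daily. Two sites recruit separately (Section 4.3). If one disregards the level and the other compares the bare number with a result in another unit, the same history could be classified differently, and neither decision could be audited against the text.

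**Working it through.** The plan reports no calculation that bears on this point, so there is no figure to reproduce. The check is one of units and then of scope.

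**1. Does the unit apply?**

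For a dissolved species, mEq/L = mmol/L × |charge|.

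- Lithium (charge 1): 0.6 mEq/L = 0.6 mmol/L × 1. The threshold is meaningful.
- Carbamazepine (charge 0): mmol/L × 0 = 0 mEq/L at any concentration. The threshold of 0.8 has no counterpart in a laboratory result.

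The only input from outside the documents is that carbamazepine is uncharged, which is basic chemistry.

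**2. Can a reader guess what was meant?**

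Three readings are possible. The first two need assumptions that are not in the documents: a molar mass of 236.27 g/mol, and usual treatment levels of 4–12 µg/mL (sensitivity range 2–15 µg/mL).

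| Reading | Threshold | Against the assumed range |
|---|---|---|
| 1 mEq treated as 1 mmol | 0.8 × 236.27 = 189 mg/L = 189 µg/mL | 189/12 ≈ 16 times the upper end (189/15 ≈ 13 times) |
| Unit replaced by µg/mL, number kept | 0.8 µg/mL | 0.8/4 = 20% of the lower end (0.8/2 = 40%) |
| Number also wrong, for example a decimal slip | Unknown | Unknown |

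Neither of the first two gives a level that separates adequate from inadequate trials under these assumptions. The third would give neither extreme. The ratio of the first two thresholds, 189.0/0.8 ≈ 236, is simply the molar mass and says nothing about enrolment.

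**3. Do the documents settle it elsewhere?**

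No. Item 4 gives levels for lithium (0.6) and Depakote (50) but leaves carbamazepine to clinician judgement. Section 6.2 lists the Antidepressant Treatment History Form among the screening assessments without reproducing its thresholds. That the unit was carried over from the lithium entry is plausible from its position, but it is an inference.

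**4. Who is affected?**

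The carbamazepine level decides a case only if all of these hold:

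- the candidate took carbamazepine for at least 4 weeks in the current episode and it failed;
- the dose was below 400 mg daily, since otherwise the dose route already qualifies;
- a blood level is available;
- none of the other 8 − 1 = 7 listed drugs supplies a qualifying trial.

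The documents do not say how many candidates meet all four. In a sample of 10 it may be none.

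**The case against.** The strongest reply is that the slip will do little in practice. The item leaves the final determination to the study team's clinicians, so a faulty level neither admits nor excludes anyone automatically. At screening a trained rater completes the treatment history form, current and lifetime, to judge whether past trials were adequate and failed, and participants are staged for treatment resistance (Section 6.2). The team then meets to confirm eligibility after record review (Section 10.3.3). A rater working from that form is unlikely to set a bare 0.8 against a laboratory report.

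Most of this stands, and it is why the point is minor. It does not cure the text: judgement can override an unusable threshold but cannot make it usable, and two sites may override it differently.

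A reader might infer something stronger: that the level route admits almost anyone or no one, and so the trial does not study the population it names. The documents do not support that.

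- *Almost anyone* could at most mean almost any patient who took carbamazepine for at least 4 weeks without success.
- *No one* could apply only to the level alternative; the dose route and seven other drugs are untouched.
- Both extremes rest on assumed treatment levels and leave out the possibility that the number is wrong too.
- That one misclassified participant would be 1/10 = 10% of the sample is true of any eligibility slip in this trial and does not show that this one occurs.

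**Conclusion.** The carbamazepine blood level in item 5 is wrong as written. It is a threshold in current eligibility text, stated in a unit that does not apply to the drug, and nothing else in the documents supplies a usable level. This rests only on carbamazepine being uncharged. The molar mass and the assumed treatment range serve to illustrate that the obvious repairs do not rescue the number; the conclusion does not depend on them.

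The effect is narrow: candidates whose only qualifying trial is carbamazepine below 400 mg daily with a level on record. No stated statistical figure changes, since the sample of 10 was chosen for feasibility and available resources (Section 9.1). Severity is minor.

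**What to change.** The sponsor should reconcile the carbamazepine level and its unit in Section 4.1, item 5 with the Antidepressant Treatment History Form that the item cites, checking the number as well as the unit. Any participant already qualified through a carbamazepine level should be rechecked against the reconciled text. No replacement value is proposed here; that is for the sponsor to take from the source.

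The cost is a one-line eligibility amendment and a review of at most 10 eligibility records.
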